10.2.3 VISIT 3 – Period 2/ DAY 30 /EXIT

1	Document wear time compliance (days, hours) and lens care compliance. Collect used study lens care product from the subject.
2	Obtain information on any changes in medical health and/or the use of concomitant medications since Visit 2.
3	Have subject complete the Subjective Questionnaire based on lenses worn and test solution used during the 30-day study period (CLDEQ-8, [REDACTED] [REDACTED] [REDACTED])

4	Conduct Snellen VA with worn lenses. For details refer to MOP.
5	[REDACTED]
6	Remove lenses and perform biomicroscopy assessments using slit-lamp examination scales. For details and order of staining procedures, refer to MOP.
7	Perform subjective (manifest) refraction assessment and BCVA assessment (as needed). For details refer to MOP.
8	Assess and record AEs that are observed or reported (see Section 12).
9	Record any device deficiencies that are observed or reported.
10	Exit the subject from the study.

10.3 Unscheduled Visits

Any visit that occurs between the regularly scheduled visits must be documented in the unscheduled visit pages of the eCRF. During all unscheduled visits, the following procedures should be conducted:

- Document wear time compliance (days, hours) and lens care compliance.
- Obtain information on any changes in medical health and/or the use of concomitant medications.
- Perform Snellen VA with lenses (as needed).
- Perform subjective (manifest) refraction (as needed).
- Perform BCVA assessment (as needed).
- Perform biomicroscopy.
- Record any AEs or device deficiencies that are observed or reported.
- Replace lenses and dispense additional study lens care solution for the study period if needed (as needed). Record all unplanned lens replacement dates in the source.
- Exit the subject from the study (if subject is discontinuing at the unscheduled visit).

If the subject is discontinuing at the unscheduled visit, the Early Exit visit eCRF should be completed rather than the eCRF form for an unscheduled visit.

10.4 Discontinued Subjects and Screen Failures

Discontinued subjects are those who withdraw or are withdrawn from the study after being randomized. Subjects may discontinue from the study at any time for any reason. Subjects

may also be discontinued from the study at any time if, in the opinion of the Investigator, their continued participation poses a risk to their health. Discontinued subjects will not be replaced (ie, their subject numbers will not be re-assigned/re-used).

If a subject is identified not to fulfill the eligibility criteria for study inclusion during the Screening visit (Visit 1), the subject will be screen failed and will not participate any further in the study. The EDC system will be updated to confirm the subject is a screen failure. The Investigator will explain to the subject the reason(s) why eligibility was not met and provide appropriate information/treatment, if required. The Exit form will be completed for all discontinued subjects and screen failures.

Should a subject exhibit any clinically relevant signs, symptoms, or other clinical observations that possibly could be associated with suspected sensitivity or intolerance to one of the study treatments, the Investigator must document those observations on an AE Form. Observations must also be reported for occurrences not associated with any study treatment (see Section 12.3, Procedures for Recording and Reporting AEs and SAEs).

Any subject who exits early from the study should undergo all procedures outlined at Visit 3/Exit. Additionally, the Exit Form must be completed and the reason for discontinuation must be identified and captured in EDC.

Finally, to ensure the safety of all subjects who discontinue early, Investigators should assess each subject and, if necessary, advise them of any therapies and/or medical procedures that might be needed to maintain their health.

10.5 Clinical Study Termination

If the clinical study is prematurely terminated or suspended, the Sponsor will inform the Investigator and the regulatory authorities of the termination/ suspension and the reason(s) for the termination/suspension. The Investigator should promptly notify the IEC/IRB of the termination or suspension and of the reasons. The Sponsor reserves the right to close the investigational site or terminate the study in its entirety at any time, for reasonable cause. Reasons for the closure of an investigational site or termination of a study may include:

- Successful completion of the study
- The study's enrollment goals are met
- The Investigator fails to comply with the protocol or GCP guidelines
- Safety concerns

- Sufficient data suggesting lack of efficacy
- Inadequate recruitment of subjects by the Investigator

The Investigator also may terminate the study at his/her site for reasonable cause. If the Sponsor terminates the study for safety reasons, it will immediately notify the Investigator(s) by telephone and subsequently will provide written confirmation of and instructions for study termination.

11 ANALYSIS PLAN

Continuous variables will be summarized for the observed values using the number of observations, mean, SD, median, minimum and maximum, as well as CIs or CLs where applicable. Categorical variables will be summarized with counts and percentages from each category. Any deviations to this analysis plan will be updated during the course of the study as part of a protocol amendment or will be detailed in the clinical study report.

11.1 Subject Evaluability

The final subject evaluability will be determined prior to breaking the code for masked lens care sequence assignment and locking the database.

11.2 Analysis Data Sets

11.2.1 Safety Analysis Set

Safety analyses will be conducted using the safety analysis set on a treatment-emergent basis. The safety analysis set will include all subjects/eyes exposed to the newly dispensed habitual lenses for the study disinfected with at least one study lens product evaluated in this study. For treatment-emergent safety analyses, subjects/eyes will be categorized under the actual lens care product exposed.

11.2.2 Full Analysis Set

The FAS is the set of all randomized subjects who are exposed to at least one of the study lens care products as defined for the Safety Analysis Set.

11.2.3 Per Protocol Analysis Set

The PP analysis set is a subset of all randomized subjects and excludes all data/subjects which have met any of the critical deviation criteria identified in the DEP.

11.3 Demographic and Baseline Characteristics

Demographic information (age, sex, ethnicity, and race) will be summarized on the safety, full, and PP analysis sets. Baseline characteristics on habitual lens and lens care information as well as activities, CLDEQ-8, [REDACTED], [REDACTED] will be summarized on the full and PP analysis sets. Due to the crossover design, demographic and baseline data will be presented by lens care sequence group and overall.

11.4 Efficacy Analyses

This study defines one primary endpoint [REDACTED] All efficacy evaluations will use the FAS as the primary analysis set. [REDACTED]

[REDACTED]

[REDACTED]

For all planned inferential analyses, alternative models/methods may be considered if convergence cannot be achieved.

11.4.1 Primary Efficacy

The primary objective of this study is to demonstrate superiority of OFPM when compared to HMPS in reducing dryness symptomatology as measured by CLDEQ-8.

The corresponding endpoint is the score (range 0 to 37) from CLDEQ-8, obtained by adding the numerical responses to each of the 8 items, collected at the Day 30 follow-up for each product (Visit 2 and Visit 3).

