2 OVERVIEW OF STUDY PLAN

	Visit 1	Visit 2	Visit 3	USV
Procedure/Assessment	Screening & Baseline Period 1/ Day 1	Period 1 Day 30 ± 3 Follow-Up Period 2/ Day 1	Period 2 Day 30 ± 3 Follow-Up/ Exit	Unscheduled Visit
Pre-Screening questionnaire (symptomatology, digital device use, and HMPS identification) ^a	X (before consent)			
Informed consent	X			
Collect demographics and activities	X			
Medical and lens/lens care history	X			
Concomitant medications/ changes in concomitant medications	X	X	X	X
Subjective (manifest) refraction ^a	X	(X)	(X)	(X)
BCVA ^a	X	(X)	(X)	(X)
Inclusion/exclusion	X			
Randomization	X			
Dispense a new pair of habitual lenses and assign/dispense the study lens care solution per randomization. Educate on instructions for use.	X	X		(X)
Snellen VA with lenses	X ^b	X ^{b, d}	X ^d	(X)
Biomicroscopy	X	X	X	X
CLDEQ-8 Questionnaire	X ^c	X	X	

	Visit 1	Visit 2	Visit 3	USV
Procedure/Assessment	Screening & Baseline Period 1/ Day 1	Period 1 Day 30 ± 3 Follow-Up Period 2/ Day 1	Period 2 Day 30 ± 3 Follow-Up/ Exit	Unscheduled Visit
Assess AEs	X ^c	X	X	
Assess device deficiencies	X	X	X	X
Document wear time compliance (days, hours) and lens care compliance ^a		X	X	(X)
Exit form	(X)	(X)	X	(X)

^aSource only

^bWith new lenses being dispensed at the visit

^cBased on habitual regimen

^dWith lenses worn for the study period.

^eAEs are collected from the time of informed consent.

(X)= as needed.

AEs=adverse events, BCVA=best corrected visual acuity, CLDEQ-8=Contact Lens Dry Eye Questionnaire-8, HMPS=Habitual multi-purpose solution, IRB=Institutional review board, USV=unscheduled visit, VA=visual acuity

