8.1 Inclusion Criteria

1. Age 45-65 (both inclusive) and must sign the informed consent.
2. Current adapted two-week/monthly replacement soft contact lens wearers (at least 2 months) with symptoms of contact lens induced dryness as defined by the Symptomatology (Eligibility) Pre-screening questionnaire.

Note: Subject may be wearing multifocal contact lenses or single vision contact lenses prescribed for monovision or for distance only.
3. Requires a near spectacle ADD of +0.50 or greater.
4. Best corrected visual acuity (BCVA) to 20/30 or better in each eye at distance at Visit 1.
5. Willing to wear lenses for a minimum of 5 days per week 6 hours per day, and attend all study visits.
6. Currently using a non-Alcon MPS to care for their lenses (at least 2 months).
7. Uses digital devices (eg, smart phone, tablet, laptop computer, or desktop computer) for 20 consecutive minutes at least twice a week and willing to continue the same pattern for the duration of the study as assessed at Pre-screening.

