11.5 Handling of Missing Data

All data obtained in evaluable subjects/eyes will be included in the analysis. No imputation for missing values will be carried out for the efficacy analysis.

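### Does the plan need a rule for a CLDEQ-8 score taken at early exit?

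*Protocol*

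**What the plan says.** Protocol 11.4.1 defines the primary endpoint as the total CLDEQ-8 score "collected at the Day 30 follow-up for each product (Visit 2 and Visit 3"). SAP 4.1 has the same definition. The hypotheses in Protocol 11.4.1.1 and SAP 4.2.1 concern the means at that follow-up, and the schedule gives a window of Day 30 ± 3.

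Protocol 10.4 adds: "Any subject who exits early from the study should undergo all procedures outlined at Visit 3/Exit". Step 3 of the Visit 3 procedures (Protocol 10.2.3) reads "Have subject complete the Subjective Questionnaire based on lenses worn and test solution used during the 30-day study period" and names the CLDEQ-8.

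Protocol 11.5 has two sentences on missing data: "All data obtained in evaluable subjects/eyes will be included in the analysis" and "No imputation for missing values will be carried out for the efficacy analysis". Evaluability is fixed before the sequence code is broken (Protocol 11.1), under a Deviations and Evaluability Plan that is not among the documents. Text is blacked out in Protocol 11.4 and after the primary model in SAP 4.3.1.

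**The concern.** The protocol collects a score at early exit that no visible sentence assigns to a solution, a period or an analysis. Read literally, a subject who leaves in Period 1 contributes no outcome, and one who leaves in Period 2 contributes only the Period 1 score. The FAS contrast is then close to a contrast among completers. The first sentence of Protocol 11.5 could be read the other way, so two analysts might build different primary datasets.

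Dryness is both the outcome and a plausible reason to leave. An entry criterion is "Currently using a non-Alcon MPS to care for their lenses (at least 2 months"), so the habitual solution is familiar and OFPM is new. If subjects who do badly on OFPM leave and their scores are dropped, OFPM looks better than it is and the one-sided 5% test rejects too often. If the excess is on the habitual solution, the bias runs against OFPM and costs power.

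**Working it through.** **1. Which reading the text supports.** The objective, endpoint and hypotheses all refer to about 30 days of use, and the visit window is Day 30 ± 3. An exit score outside that window is therefore not an observation of the endpoint. The all-data sentence in Protocol 11.5 is a general inclusion rule and does not redefine the endpoint.

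**2. Whether the exit score is captured.** The "CLDEQ-8 Questionnaire" row of the schedule is blank for unscheduled visits, and the list in Protocol 10.3 omits it. For a subject who discontinues at such a visit, however, Protocol 10.3 says "the Early Exit visit eCRF should be completed rather than the eCRF form for an unscheduled visit", and Protocol 10.4 then requires the Visit 3 procedures. The two sections fit together. Protocol 10.4 also requires the reason for discontinuation to be recorded.

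**3. The plan's own sample size.** Inputs from Protocol 11.10: SD of paired differences 10, difference 3, one-sided 0.05, power 80%. Normal approximation: N = (10 × (1.645 + 0.842) / 3)² = 68.7. With the noncentral t on N − 2 degrees of freedom the minimum is 71, which becomes 72, or 36 per sequence, with power about 81%. The stated figure reproduces.

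**4. Scale of the possible bias.** About 120 are randomised and 110 complete (Protocol 8), so about 10 are lost. As an approximation, treat the estimate as the mean paired difference among completers.

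- Standard error: 10 / √110 = 0.953.
- If the lost subjects' mean paired difference (OFPM minus HMPS) lies Δ above the overall mean, the completers' mean shifts by −Δ × 10/110 = −0.091Δ.
- A false 3-point difference would need Δ = 3 × 11 = 33 points, on a scale that runs from 0 to 37.
- With no true difference and a shift b, one-sided rejection is Φ(−1.645 − b/0.953).

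**5. Simulated shifts set against that formula.** The simulations fit the stated crossover model to 120 subjects with no true difference. Assumed SDs: subject 6, subject-specific treatment difference 5, residual 6. The paired-difference SD is then √(25 + 2 × 36) = 9.85, close to the plan's 10. Exits are given as OFPM/HMPS. In the first four rows all ten are dryness-driven and come from the worst quartile of scores on the solution in use. In the last three, the rest of the ten leave at random.

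| Exits | Shift b | Simulated rejection | Formula |
|---|---|---|---|
| 5/5 | 0.00 | 5.0% | 5.0% |
| 7/3 | −0.30 | 9.7% | 9.2% |
| 10/0 | −0.73 | 19.6% | 19.0% |
| 0/10 | +0.67 | 0.9% | 0.9% |
| 2/1 worst quartile, 7 random | −0.05 | 5.1% | 5.6% |
| 3/1 worst quartile, 6 random | −0.14 | 7.0% | 6.7% |
| 4/2 worse half, 4 random | −0.07 | 5.8% | 5.8% |

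The 10/0 row corresponds to Δ = 0.73 × 11, or about 8 points. A second set of simulations (between-subject SD 5, within-subject SD 10/√2) gives −0.4 to −0.6 and 11–15% at 8/2, and −0.7 to −1.1 and 18–29% at 10/0. Its 5/5 case stays near zero, with 4–4.5%.

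**6. What adding exit scores would do.** If the exit score equals the Day 30 score the subject would have had, every split returns to about zero, with error of 4.6–5.3%. If it lies halfway between baseline and Day 30, 7/3 still gives −0.12 and 6.5%, and 10/0 gives −0.26 and 8.9%. Scores from shorter exposure therefore remove only part of the bias, and they answer a slightly different question.

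**The case for a change.** The best counter-argument is that a moderate imbalance is enough to matter. At 7/3 the error roughly doubles, and the claim rests on a single one-sided test. Nor does imbalance need subjects to treat the solutions differently. Suppose a subject has a 50% chance of leaving when the score is at least 12 points worse than baseline, on either solution. That yields 6.3 exits on OFPM and 4.3 on the habitual solution on average, a shift of −0.28 and 9.1% rejection. In the other direction, with a true difference of −3, a 0/10 split lowers power from about 94% to 80%, or to 65–77% under the second set of assumptions. One assignment sentence and one extra model run would cost little.

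The mechanism is real, and the visible text has no assignment rule; that much stands. The size is less secure. The allowance of ten covers losses for any reason, and nothing in the documents ties it to dryness. The same-rule result falls to +0.02 and 4.7% if subjects do not differ in their response to the solutions, and grows to −0.71 and 19.9% if that SD is 8; the documents give no such figure. An excess on OFPM is also uncertain: subjects are enrolled because they have dryness symptoms while on their habitual solution, and Protocol 5.2 lists the same potential side effects for both.

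The low cost does not settle the matter either. The sensible remedy keeps the Day 30 model as primary, so it gives readers context but does not correct the primary test.

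**Conclusion.** No change is needed. This is a missing detail that the endpoint definition largely settles: an exit score outside the Day 30 window stays out of the primary model. Analysts can be expected to attribute it to the solution and period in use at exit if they use it in support, and to tabulate exits by solution and reason. The blacked-out text or the Deviations and Evaluability Plan may already say so.

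At the planned loss of about 10 in 120, the shift is about zero when exits are balanced, and 0.05 to 0.14 points in the mixed-cause cases. That compares with a standard error of about 0.95 and a design difference of 3. Shifts of 0.3 points or more arose when all the exits were dryness-driven and either clearly unbalanced or made so by a common quitting rule with marked variation in response. They can run in either direction. These sizes rest on assumed exit patterns and variance components, since the documents give only the paired-difference SD and the numbers randomised and completed. Losses well above ten, or a marked excess on one solution, would call for a supportive analysis when the results are read.

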11.4.1.1 Statistical Hypotheses

The null and alternative hypotheses are formulated as follows:

$$H_0: \mu_{(\text{OFPM})} - \mu_{(\text{HMPS})} \geq 0$$

$$H_a: \mu_{(\text{OFPM})} - \mu_{(\text{HMPS})} < 0$$

where $\mu_{(\text{OFPM})}$ and $\mu_{(\text{HMPS})}$ denote the mean CLDEQ-8 score for OFPM and HMPS, respectively, at the Day 30 follow-up.

11.4.1.2 Analysis Methods

A mixed effect repeated measures model will be fit to test these hypotheses, including terms for lens care solution, period, sequence group, and baseline CLDEQ-8 as fixed effects and subject as a random effect. Lens care difference (OFPM minus HMPS) and the corresponding one-sided 95% upper confidence limit will be provided.

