8 SUBJECT POPULATION

Approximately 120 subjects (approximately 8 to 20 subjects per site) are to be randomized at approximately 8 United States (US) sites to achieve approximately 110 subjects completed. An advertisement may be used to aid recruitment. The advertisement will be submitted to the IEC/IRB for approval. The IRB approved Pre-screening questionnaire will be provided before taking the consent.

The enrollment for the study is planned for 6 weeks. The expected duration of subject participation in the study (3 scheduled visits) is 30 ± 3 days per study period (up to 66 days total). The complete inclusion and exclusion criteria are presented in Section 8.1 and Section 8.2.

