9 TREATMENTS ADMINISTERED

Upon completing the Pre-screening Questionnaire and satisfying the relevant pre-screening criteria, subjects will sign informed consent and then be considered enrolled into the study. A subject ID number will be assigned to enrolled subjects by entering the subject into the electronic data capture (EDC) system. Subjects eligible after Screening at Visit 1 will be randomized (1:1) to receive either OFPM or HMPS to care for their lenses in Period 1 of the study. For Period 2, the contact lens solution that was not allocated for use in Period 1 will be dispensed. Throughout the study, designated unmasked site personnel at the investigational site will be responsible for the accounting of all study products and will ensure that the study products are not used in any unauthorized manner.

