9.4 Subject Confidentiality and Methods Used to Minimize Bias

The Investigator must ensure that the subject's anonymity is maintained throughout the course of the study. In particular, the Investigator must keep an enrollment log with confidential identifying information that corresponds to the subject numbers and initials of each study participant. At the end of the clinical study, the Sponsor will collect a copy of the enrollment log without any identifying subject information. All documents submitted to the Sponsor will identify the subjects exclusively by subject ID and demographic information. No other personally identifying information should be transmitted to the Sponsor.

The intent of masking is to limit the occurrence of conscious and unconscious bias in the conduct and interpretation of the clinical study. Bias could arise from the influence that the knowledge of a specific treatment assignment may have on the recruitment and allocation of subjects, their subsequent care, the assessment of end points, the handling of withdrawals, and so on. The essential aim of masking, therefore, is to prevent identification of the test article(s) by the Investigator, subject, and others associated with the conduct of the study until all such opportunities for bias have passed.

This study is Investigator-masked and subject quasi-masked (masked to test solution brand only), with subjects randomized to the order in which they will use OFPM and their HMPS for 30 ± 3 days each. The Investigator will not be aware of the specific treatment being administered and the subject will not be aware of the brand of the test solution. Alcon study personnel will be masked, with the exception of the following: Study monitor, Lead CSM, and person responsible for generating the randomization schedule. This level of masking will be maintained throughout the conduct of the study. Subjects will be assigned treatment order based on the randomization schedule; it will be blocked to ensure a balance of study treatment allocations within investigational sites. The randomization scheme will be generated and maintained by the Sponsor. In the event of a medical emergency where the knowledge of subject treatment is required, an individual Investigator will have the ability to unmask the treatment sequence assignment for a specific subject.

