11.10 Sample Size Justification

Sample size calculation for each of the relevant efficacy endpoints is described below.

Primary Efficacy:

Sample size calculation for the primary efficacy hypothesis on decrease in symptomatology is based on published data (Chalmers 2012). With an assumed SD for paired differences of 10, a sample size of 36/sequence will provide 80% power to detect a difference of 3 at one-sided $\alpha=0.05$.

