### **1.3              Randomization**

A member of the Randomization Programming group at Alcon who is not part of the study team will generate the randomized allocation schedule(s) for study contact lens solution assignment. Subjects eligible after screening at Visit 1 will be randomized (1:1) to receive either OFPM or HMPS to care for their lenses in Period 1 of the study. For Period 2, the contact lens solution that was not allocated for use in Period 1 will be dispensed.

Randomization will be blocked to ensure a balance of study treatment (lens care sequence) allocation within investigational sites. Randomization will be implemented in an Electronic Data Capture (EDC) system.

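### Sequence is blocked within sites, but the primary model has no site-by-period term, so the standard error is slightly too wide if the period change differs between sites

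*Protocol*

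**What the plan says.** **Randomisation.** Protocol section 9 says that eligible subjects "will be randomized (1:1) to receive either OFPM or HMPS to care for their lenses in Period 1" and cross to the other solution in Period 2. SAP 1.3 adds: "Randomization will be blocked to ensure a balance of study treatment (lens care sequence) allocation within investigational sites". Protocol 9.4 says the same of the schedule: "it will be blocked to ensure a balance of study treatment allocations within investigational sites". Site is therefore a randomisation stratum. Block size is not stated.

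**Size.** Protocol section 8: "Approximately 120 subjects (approximately 8 to 20 subjects per site) are to be randomized at approximately 8 United States (US) sites". The target is about 110 completers.

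**Primary model.** Protocol 11.4.1.2 and SAP 4.3.1 give the same list of terms: "including terms for lens care solution, period, sequence group, and baseline CLDEQ-8 as fixed effects and subject as a random effect". The result is the OFPM minus HMPS difference with a one-sided 95% upper confidence limit. Neither site nor site-by-period is listed, and the visible text gives no reason. Some SAP text after the model description is redacted, but the term list is complete in both documents.

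**Sample size.** Protocol 11.10 (and SAP section 7): "With an assumed SD for paired differences of 10, a sample size of 36/sequence will provide 80% power". The design effect is 3 points and the test is one-sided with an alpha of 0.05.

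**The concern.** In a two-period crossover, a constant difference between sites cancels from each subject's pair of scores. A difference between sites in the change from Visit 2 to Visit 3 does not cancel. It could come from local season, staff or the way the questionnaire is given.

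Blocking handles this variation in the design. When each site has equal numbers in the two sequences, a site's own period change affects both sequences alike and drops out of the treatment contrast. The planned model allows only one common period effect, so the site-to-site spread goes into the residual variance and from there into the standard error.

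At stake is precision: the upper limit that decides superiority would be wider than the design earns. Bias and false-positive risk are not at stake.

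**Working it through.** **1. Reproduce the plan's figure.** The treatment effect is half the difference between the two sequences' mean period differences, so its standard error with n complete pairs in balance is SD/√n.

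- 36 per sequence: 10/√72 = 1.179. Noncentral t with 70 df, noncentrality 3/1.179 = 2.55: power 0.809.
- 35 per sequence: power 0.7996. So 36 is the smallest number that reaches 80%, and the plan's figure reproduces.
- At the planned 110 completers: 10/√110 = 0.953, power 0.931.

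**2. Set up the comparison.** Take 8 sites × 14 completers = 112 pairs, 7 per sequence in each site (an idealisation of the planned numbers). Hold the SD of paired differences at 10, as in the plan. Let T be the between-site SD of the period change. **T is an assumption**; the documents give no value.

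- Within-site variance: 100 − T².
- True standard error under blocking: √((100 − T²)/112).
- Planned model: the expected between-site sum of squares is 14 × 7 × T² = 98T², spread over 112 − 2 = 110 df. Its expected residual variance is therefore (100 − T²) + (98/110)T².
- With site-by-period: the residual variance is 100 − T² on 112 − 9 = 103 df.
- One-sided error of the planned test: Φ(−1.645 × SE ratio).
- Power at effect d: Φ(d/true SE − 1.659 × SE ratio) as planned, and Φ(d/true SE − 1.660) with the term (t quantiles for 110 and 103 df).

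| T | Planned SE | True SE | Ratio | One-sided error | Power at 3 points, planned → with term | Power at 2 points, planned → with term |
|---|---|---|---|---|---|---|
| 0 | 0.945 | 0.945 | 1.000 | 5.0% | 93.5% → 93.5% | 67.6% → 67.6% |
| 1 | 0.944 | 0.940 | 1.005 | 4.9% | 93.6% → 93.7% | 67.8% → 68.0% |
| 2 | 0.943 | 0.926 | 1.018 | 4.7% | 94.0% → 94.3% | 68.1% → 69.2% |
| 3 | 0.940 | 0.901 | 1.043 | 4.3% | 94.5% → 95.2% | 68.7% → 71.2% |
| 4 | 0.937 | 0.866 | 1.082 | 3.8% | 95.3% → 96.4% | 69.7% → 74.2% |

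Example, T=3: planned residual variance 91 + 0.891 × 9 = 99.02; √(99.02/112) = 0.940; √(91/112) = 0.901; ratio 1.043.

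**3. Check by simulation.**

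- Same layout, 8,000 replicates. T=3: mean SE 0.937 against about 0.90, error 4.4%, power at 2 points 68% → 71%. T=4: 0.934 against 0.864, error 3.6%, power at 2 points 70% → 74%.
- Unequal sites of 8 to 20, blocks of 4, 8% dropout. The planned SE is about 4% larger than with the term at T=3 and 7% at T=4, with error about 4.2% and 3.8%. At T=0 the term moves the SE only from 0.950 to 0.954.
- 110 completers, blocks of 2 or 4, T=3.16 (10% of variance). Power at 3 points is 0.937 to 0.941 without the term and 0.945 to 0.948 with it.

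**4. Which term does the work?** Mixed models on 112 simulated subjects, T=3.16, 40 runs: mean SE 0.932 as planned, 0.930 with a site main effect only, 0.892 with site-by-period. The site main effect alone leaves the problem in place.

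**The case against.** The strongest reply is that the harm depends wholly on T, and nothing in the documents shows that T exceeds zero. T=3 would make the between-site SD of the drift as large as the 3-point effect the trial is sized to detect, on a scale of 0 to 37. Enrolment is planned for 6 weeks, both periods last about 30 days, and new habitual lenses are dispensed for each, so large site-specific drifts are not obviously expected. At T of 2 or less the table shows almost nothing, and power at 3 points is already about 93%. All of this stands, and it is why the priority is low.

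A second reply is that sites are small and unequal, and dropout will disturb the balance, so fixed site-by-period terms could cost more than they return. The simulation with unequal sites and dropout does not bear this out: at T=0 the SE rises by 0.004. A site left with only one sequence adds nothing to the complete-pair contrast, and the model can still be fitted.

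Third, redacted text may describe supportive analyses that deal with site. That cannot be ruled out, but the primary model's own term list is printed in full.

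A reader might infer that leaving out a stratification factor makes the primary test invalid or a superiority claim doubtful. The documents do not support that. Balanced allocation leaves the estimate unbiased, and the error in the SE runs in the conservative direction.

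**Conclusion.** The point holds as a conditional and modest loss of efficiency. The design blocks on site and the primary model does not use it. If the period change varies between sites, the upper limit is too wide by nothing at T=0, under about 2% in SE for T up to 2, about 4% at T=3 and 7 to 8% at T=4. At T=3 to 4 the power forgone is about 1 point at the 3-point design effect and 2 to 4 points at a 2-point effect. The one-sided error falls to about 4% and does not rise above 5%.

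These figures rest on the plan's SD of 10, about 8 sites, about 110 complete pairs and an assumed T. Two further inferences are not supported: that the trial is underpowered for this reason, and that a site main effect would cure the SE. The gain matters most if the true effect is below 3 points.

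**What to change.** In Protocol 11.4.1.2 and SAP 4.3.1, add site and site-by-period as fixed effects to the primary model. For complete pairs this is the regression of the Visit 2 minus Visit 3 difference on sequence and site. Keep the site main effect alongside the interaction: the full analysis set can include subjects with data from one period only, without imputation, and for them site does not cancel. If the sponsor prefers the present model, one sentence should say why site is left out.

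The hypotheses, alpha and upper-limit rule stay as they are. The cost is a sentence in each document, no new data, and about 7 of roughly 108 residual degrees of freedom at 110 completers. The choice should be fixed before unmasking, because adding the term afterwards could look data-driven.
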